2. VERSION HISTORY

Version	Date	Author	Comment / changes
0.1	22/05/2019	RCTs	Initial draft version (based on protocol version 4.0 dated 18OCT2018 and CRF version 6.0 dated 13DEC2018 and Local Care CRF version 5.0 dated 17OCT2017 and planimetry forms dated 09FEB2018 and 06APR2018)
0.2	13/06/2019	RCTS	Integration of Sponsor's comments
1.0	14/06/2019	RCTS	First approved and signed version
1.1	13/08/2020	RCTs	Update of the primary endpoint analysis
2.0	10/12/2020	RCTs	Second approved and signed version

Statistical Analysis Plan	Dago 6 /
Version 2.0 – 10/12/2020	Page 6 /

22

3. ABBREVIATIONS

Suprasorb®C (Lohmann & Rauscher)

Abbreviation	Description
AE	Adverse Event
ATC	Anatomical Therapeutic Chemical
CI	Confidence Interval
CRF	Case Report Form
PMCF	Post Market Clinical Follow up
TS	Treated Set
MedDRA	Medical Dictionary for Regulatory Activities
OQOL	Overall Quality of Life
PPS	Per Protocol Set
PT	Preferred term
Q1	First quartile
Q3	Third quartile
QOL	Quality of Life
SAP	Statistical Analysis Plan
SD	Standard Deviation
SOC	System Organ Class
WHAT	Wound Healing Analysing Tool
WHO-DD	World Health Organization Drug Dictionary

Statistical Analysis Plan
Version 2.0 – 10/12/2020

4. PROTOCOL

This Statistical Analysis Plan is based on the Suprasorb® C Protocol version 4.0 dated 18OCT2018.

The overall study design, plan description, study objectives, inclusion and exclusion criteria and sample size calculation are presented in the protocol.

5.2. Analysis subgroups

No subgroup is defined.

Relative change in wound area from baseline to W8 ≤ -15% (yes/no):

This endpoint will be derived as follows:

- Yes, if relative change in wound area from baseline to $W8 \le -15\%$.
- No, if relative change in wound area from baseline to W8 > -15%.

Shift from the healing phase to the granulation phase:

The parameter "shift of phase" will be analysed by Lohmann & Rauscher. However, to compute the combined primary endpoint, the following endpoints will be computed:

Relative change in granulation from baseline to W8 (%) = 100 x (granulation at W8-W0) / W0.

This endpoint will be derived as follows:

- Yes, if relative change from baseline in granulation to W8 > 50%.
- No, if relative change from baseline in granulation to W8 ≤ 50%.

Note:

Granulation (%) of the wound area has been measured by an independent expert using photos. Granulation data of each patient at each visit will be sent by Lohmann & Rauscher to RCTs. RCTs will import the granulation data into the SAS database. Please refer to the Data Transfer Specifications for further details.

6.2. Secondary endpoints

Secondary endpoints are:

• Duration of Suprasorb® C use (days): date of last removal of Suprasorb® C^[1] – date of inclusion +1

[1] Date of last removal of Suprasorb® C =

- Date of last removal of Suprasorb® C at D28 assessment if 'Healing of the wound' ticked "Yes" at assessment at D28
- Or Date of last removal of Suprasorb® C at D56 assessment if 'Healing of the wound' ticked "Yes" at assessment at D56
- Or the most recent date among: Date of assessment at D56 (i.e. date of last assessment) and
 Date of study withdrawal before D56*

* Some patients have both a date of study withdrawal and a date of assessment at D56

If date of last removal of Suprasorb® C is filled at D28 and D56, the most recent date will be used.

All secondary endpoints relative to safety, adverse events or side effects are described in section 6.3. Safety endpoints

6.3. Safety endpoints

6.3.1. Adverse events

Adverse events will be coded using the MedDRA dictionary (version 21.1).

Safety will be evaluated by the frequency and nature (SOC/PT) of adverse events (AEs) (non serious and serious) and serious adverse events (SAEs):

All adverse events (AE)

- Serious adverse events (SAE)
- AE by severity (mild/moderate/severe)
- AE with certain, probable or possible causal relationship with Suprasorb® C
- AE with certain, probable or possible relationship with the study procedure

AEs will be reviewed during data review meeting to decide whether they correspond to known risk and side effects (i.e wound infection, allergic disorders, pain and maceration).

A description of the following endpoints will be presented:

- At least one AE derived variable
- At least one SAE derived variable
- Time to onset (days) derived variable
- Outcome (resolved / ongoing)
 - If resolved, duration (days) derived variable
- Severity (mild / moderate / severe)
- Causal relationship to Suprasorb® C (Certain / Probable / Possible / Improbable / Excluded)
- Related to Suprasorb® C (Yes / No) derived variable
 - Yes if Certain or Probable or Possible or Improbable
- Causal relationship to study procedure (Certain / Probable / Possible / Improbable / Excluded)
- Related to study procedure (Yes / No) derived variable
 - Yes if Certain or Probable or Possible or Improbable

Individual listing of AEs and SAEs will be provided.

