11 SAFETY AND EVENT HANDLING

The following definitions on the basis of DIN EN ISO 14155:2012-01 will be employed:

Adverse event (AE)

Any untoward medical occurrence, unintended disease or injury, or untoward clinical signs (including abnormal laboratory findings) in subjects, users or other persons, whether or not related to the investigational medical device.

Adverse device effect (ADE)

Adverse event related to the use of an investigational medical device.

Serious adverse event (SAE)

Adverse event that

- a) led to death,
- b) led to serious deterioration in the health of the subject, that either resulted in
 - 1) a life-threatening illness or injury, or
 - 2) a permanent impairment of a body structure or a body function, or
 - 3) in-patient or prolonged hospitalization, or
 - 4) medical or surgical intervention to prevent life-threatening illness or injury or permanent impairment to a body structure or a body function,
- c) led to foetal distress, foetal death or a congenital abnormality or birth defect

Serious adverse device effect (SADE)

Adverse device effect that has resulted in any of the consequences characteristic of a serious adverse event.

Device deficiency

Inadequacy of a medical device with respect to its identity, quality, durability, reliability, safety or performance.

Device deficiencies that did not lead to an adverse event but could have led to a medical occurrence

- a) if either suitable action had not been taken,
- b) if intervention had not been made, or
- c) if circumstances had been less fortunate,

shall be handled as specified for SADEs. These events are defined as device deficiencies with SADE potential.

Events that are assessed as SADE or device deficiencies with SADE potential by the investigators might match the definition of a reportable event.

Incidents

Any malfunction or deterioration in the characteristics and/or performance of a device, as well as any inadequacy in the labeling **or** the instructions for use which might lead to or might have led to the death of a patient, or USER or of other persons or to a serious deterioration in their state of health. (Directive 93/24 EEC)

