8.7.1. Adverse events

Overall summary table:

For all AE categories defined in Section 6.3.1, the number of patients who experienced at least one AE of the corresponding category will be provided overall, on the TS, using the template provided in section 11.5.

All AEs will be listed.

All SAEs will be listed.

Analysis by SOC and PTs:

For all AE categories defined in Section 6.3.1, a descriptive analysis by SOC and PT will be provided on the TS, overall. Tables will summarize the total number of events and the number and percentage of patients experiencing the event. The SOC will be sorted alphabetically, and PT will be sorted by descending frequency (within SOC, on « total » column) according to the MedDRA classification (System Organ Class and Preferred Term).

The template provided in section 11.6 will be used.

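### SAP 6.3.1 defines a related adverse event in two incompatible ways: events rated improbable are outside the reporting categories but inside the derived Yes/No variables

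*SAP*

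**What the plan says.** SAP 6.3.1 rates causality on five levels: certain, probable, possible, improbable and excluded. It uses that scale separately for the device and for the study procedure.

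The section first lists the categories in which events are to be reported. Two of them concern relatedness: "AE with certain, probable or possible causal relationship with Suprasorb® C" and "AE with certain, probable or possible relationship with the study procedure".

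Further down, under "A description of the following endpoints will be presented", it lists the five-level ratings and, after each, a derived Yes/No variable for relatedness. Both derived variables carry the same rule: "Yes if Certain or Probable or Possible or Improbable".

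SAP 8.7.1 says which outputs use the categories. The overall summary gives "For all AE categories defined in Section 6.3.1, the number of patients who experienced at least one AE of the corresponding category", using template 11.5. The second set of tables is specified as "For all AE categories defined in Section 6.3.1, a descriptive analysis by SOC and PT will be provided on the TS, overall", using template 11.6. In template 11.5 the rows for events related to the product and to the procedure do not state which causality levels they include. SAP 7.6 treats an event with missing relationship as related and is silent on improbable.

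**The concern.** A report should give one answer to how many events were related to the product. Here a programmer who follows the text exactly produces two. The tables built on the categories leave improbable events out, and the described Yes/No variable counts them in. The same happens for relation to the procedure. Nothing in the SAP says which figure is the prespecified one. Because the related rows of template 11.5 name no levels, someone working from the template and the derived variable could also fill the summary table under the wider rule without noticing the conflict.

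At stake is the consistency of a reported safety figure, and the freedom to choose between two definitions once the data are known.

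**Working it through.** There is no planned figure to reproduce, so the check compares texts. Each causality level is passed through both rules of SAP 6.3.1. The result is the same for device and procedure.

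| Investigator's rating | Reporting category | Derived Yes/No variable |
|---|---|---|
| Certain | related | related |
| Probable | related | related |
| Possible | related | related |
| Improbable | **not related** | **related** |
| Excluded | not related | not related |

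The rules differ on exactly one level of five.

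*Size of the gap in events.* Let c, p, o and i be the numbers of events rated certain, probable, possible and improbable, and m the number with missing relationship, taken as related under both rules because of SAP 7.6.

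- Category count = c + p + o + m
- Derived-variable count = c + p + o + i + m
- Difference = i

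*Size of the gap in patients.* The difference is the number of patients who have at least one improbable event and no event rated certain, probable or possible or with missing relationship.

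Neither document gives adverse event rates or a breakdown by causality, so i cannot be estimated.

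*Which output uses which rule.* SAP 8.7.1 ties the overall summary and the SOC/PT tables to the categories of 6.3.1, which is the narrower rule. SAP 6.3.1 itself requires the derived variables to be presented, which is the wider rule. SAP 8.6 also announces a descriptive analysis of endpoints, but points to a section 6.3.12 that does not appear in the text supplied; I assume 6.3.1 is meant. It is certain that both rules are in force. Which table shows which count is an inference, most directly that the summary and SOC/PT tables follow the narrower one.

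*Search for a reconciling statement.* SAP 7.6 covers missing values only. Section 9, on changes from the protocol, does not mention relatedness. The related rows of template 11.5 give no levels, and the content of template 11.6 is not in the text supplied.

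**The case against.** The case against giving this much weight has four parts.

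**Counting all but excluded events as related can be a deliberate, cautious convention.** SAP 7.6 leans the same way on missing values. This stands to the extent that the documents do not show which rule was intended. It does not remove the conflict, because the categories in the same section apply the opposite convention.

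**The main tables are consistent.** On the direct reading of SAP 8.7.1, the overall summary and SOC/PT tables both use the narrower rule. This stands. The discrepancy is between those tables and the described Yes/No variable.

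**The report would be transparent.** The full five-level distribution and individual listings are also planned, so a reader could recount under either rule. This limits the harm but does not say which count is the prespecified result.

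**The SAP belongs to another study.** Section 4 bases it on the Suprasorb C protocol, its templates have a single total column, and section 7.2 plans no formal comparison. This stands too, and that mismatch is a larger matter than this one.

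A reader might infer two stronger points, which the documents do not support:

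- *That the wider rule contradicts the Protocol's definition of an adverse device effect.* Protocol section 11 says only "Adverse event related to the use of an investigational medical device". It sets no causality threshold, and the Protocol contains no five-level scale, so it does not classify an improbable event either way.
- *That the wider rule would inflate the device-effect rate in the Lomatuell Pro versus UrgoTul trial and mask a difference between arms.* That trial's device effects are not shown to be derived from this variable, and any rate on its 84 patients per arm would be invented. Masking would also depend on the measure. With assumed counts of 8 v 2 patients and 6 improbable-only patients added to each arm, the counts become 14 v 8. The ratio falls from 8/2 = 4.0 to 14/8 = 1.75, but the difference stays at 8 − 2 = 14 − 8 = 6 patients.

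**Conclusion.** The inconsistency is real and lies wholly within SAP 6.3.1. Relatedness has two definitions, for device and for procedure, and nothing in the SAP text supplied reconciles them. Followed as written, the described Yes/No endpoint exceeds the category count by the number of improbable events. That number is unknown, and it could be zero if no event is so rated.

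The consequence is limited to descriptive safety reporting. No hypothesis test, sample size or primary conclusion depends on it. The documents show that the rules differ, not that the wider one is wrong. The conclusion rests on reading the category list and the derived variables as both operative, which is how 6.3.1 and 8.7.1 present them. It is worth correcting because the change is nearly free and alters a reported safety figure.

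**What to change.** State one definition of related, for both device and procedure, and use it for the categories and derived variables of SAP 6.3.1 and for templates 11.5 and 11.6.

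- *Smallest edit.* Set both derived variables to Yes for certain, probable or possible (or missing, as in 7.6) and to No for improbable or excluded. This matches the existing categories and leaves 8.7.1 untouched. Since 7.6 names only the study drug, say explicitly that missing relationship to the procedure is handled the same way.
- *If the wider rule is intended.* Add improbable to both categories, and say that this is deliberate.
- *Either way.* Print the included levels in the related rows of template 11.5, and in template 11.6 where it tabulates related events.

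Make the choice before the data are analysed. The cost is two lines of wording, one derivation applied twice, and the row labels. Under the smallest edit the Yes/No figure falls by the improbable events and agrees with the category tables; under the wider rule the category counts rise by the same number.

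Any SAP written for the Lomatuell Pro versus UrgoTul trial should carry the same single definition, because the Protocol gives no causality cut-off of its own.

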6.4. Other endpoints and variables

6.4.1. Demographic data and other baseline characteristics

The following standard characteristics (gender, age, etc.) will be used as recorded in the CRF:

- Demographic data
 - Sex (Male/Female)
 - Age (years)
 - Weight (kg)
 - Height (cm)
 - BMI (kg/m²) derived variable
 - BMI=Weight/Height²
 - BMI will be classified as follows derived variable
 - <18.5 = underweight
 - [18.5-24.9] = Healthy weight
 - [25-29.9] = Overweight
 - >30 = Obesity
- Characteristics of target ulcer at baseline (i.e. inclusion visit)

The following characteristics will be used as recorded in the CRF:

• Appearance of wound.

- Length × width (cm²) (categorical variable)
- Exudation of wound (None / Mild / Moderate / Severe)
- Color segmentation (%)
 - Closed wound;
- Pink ± red;
- Only red;
- ± yellow/white;
- ± black
- Perilesional skin (Normal or Erythematous, Oedematous, Macerated, Eczema, Other)
 - In addition, a concatenation of all possible abnormal perilesional skin will be derived.
- Planimetric assessment of wound
 - Performed (Yes/No)
 - Largest diameter of wound (cm)
- Depth of the wound (cm)
- Pictures of wound
 - Pictures of wound after cleansing with saline solution (Yes/No)
 - If no, the main reason.
- Indication of use of Suprasorb® C (venous ulcer / mixed ulcer)
- Removal of primary wound dressing on D0:

The following characteristics will be used as recorded in the CRF:

- Presence of the wound dressing at inclusion (Yes/No)
- Bleeding of the wound when the dressing was removed (Yes/No)
- If yes, the bleeding was (mild, moderate, severe, very severe)
- Local treatment of target ulcer on D0:
 - Local treatment provided
 - Wound cleansing with saline solution (Yes/No)
 - Debridment of the wound (Yes/No)
 - Removal of fibrin/slough (Yes/No)
 - Local or oral analgesia provided prior to treating the wound (Yes/No)
 - Placement of Suprasorb® C
 - Number of dressings applied (One/Two/Three)
 - Numerical variable derived variable
 - Was the dressing cut to size before application? (Yes/No)
 - Was the dressing moistened before application? (Yes/No)
 - Ease of application (Very easy/Easy/Difficult/Very difficult)
 - Conformability to wound (Very good/Good/Poor/Very Poor)
 - If any boxes of 3 or 4 are ticked, specify the reason
 - Did the dressing overlap the perilesional skin? (Yes/No)
 - Material used for the secondary dressing (Compresses/Gauze, Absorbent dressing pad, Superabsorber, Gel, Other material, Foam, Fixation, Hydrocolloid, Film)
 - If other, specify
 - Was the compression applied? (Yes/No)

- If yes, specify the tradename
- Quality of life
 - Pain Score (1 to 10) + numerical derived variable
 - Mobility (1 to 10) + numerical derived variable
 - Social life (1 to 10) + numerical derived variable
 - Psychic aspect (1 to 10) + numerical derived variable
- Overall quality of life
 - How is your quality of life? (1 to 10) categorical and numerical variables
 - How satisfied are you with your overall quality of life? (1 to 10) categorical and numerical variables
- Planimetry
 - Wound perimeter (cm): mean of 1st data entry and 2nd data entry (*derived variable*)
 - Wound surface area (cm²): mean of 1st data entry and 2nd data entry (derived variable)

6.4.2. Other endpoints

6.4.2.1. Assessment since the last visit (day 28 and day 56)

- Healing of the wound
 - Healing of the wound (Yes/No)
 - if yes, time from inclusion to healing (days): Date of healing* Date of inclusion + 1
- * : date of healing=minimum date between date of healing at D28 , premature withdrawal if the wound has healed and date of healing at D56.

6.4.2.2.Characteristics of target ulcer at each visit (day 28 and day 56)

The following characteristics will be used as recorded in the CRF.

- Appearance of the wound
 - Length × width (cm²) categorical variable
 - Exudation of wound
 - Color segmentation (%)
 - Perilesional skin (Normal, Erythematous, Oedematous, Macerated, Eczema, Other)
- · Planimetric assessment of wound
 - Planimetric assessment performed? (Yes/No)
 - If no, specify the main reason
 - If yes:
 - Wound perimeter (cm): mean of 1st data entry and 2nd data entry (*derived variable*)
 - Change from baseline in wound perimeter (cm): Wound perimeter at D28/D56 Wound perimeter at baseline (*derived variable*)
 - Wound surface area (cm²): mean of 1st data entry and 2nd data entry (*derived variable*)
 - Change from baseline in wound surface area (cm²): Wound surface area at D28/D56 –
 Wound surface area at baseline (derived variable)
- Depth of the wound (cm)

- Change from baseline in depth of wound (derived variable)
- Picture of wound
 - Two pictures of wound after cleansing with saline solution (Yes/No).
 - If no, specify the main reason

6.4.2.3.Removal of Suprasorb® C (day 28 and day 56)

The following characteristics will be used as recorded in the CRF.

- Rests of Suprasorb® C to the wound surrounding skin? (Yes/No)
- Removal of Suprasorb® C from the wound edges possible? (Yes/No)
- Removal of Suprasorb® C residues from the wound possible? (Yes/No)

6.4.2.4.Local treatment of target ulcer (day 28 and day 56)

The following characteristics will be used as recorded in the CRF.

- Local treatment provided
 - Was the wound cleaned with saline solution? (Yes/No)
 - Was the wound debrided? (Yes/No)
 - Was fibrin/slough removed? (Yes/No)
 - Was local or oral analgesia provided prior to treating the wound? (Yes/No)
- Placement of Suprasorb® C
 - Suprasorb® C applied on D28/D56? (Yes/No)
 - If no, specify the main reason
 - If yes,
 - How many dressings were applied (One/Two/Three) + numerical derived variable
 - Was the dressing cut to size before application? (Yes/No)
 - Was the dressing moistened before application? (Yes/No)
 - Ease of application (Very easy/Easy/Difficult/Very difficult)
 - Conformability to wound (Very good/Good/Poor/Very Poor)
 - If any boxes of 3 or 4 are ticked, specify the reason
 - Did the dressing overlap the perilesional skin? (Yes/No)
 - Material used for the secondary dressing (Compresses/Gauze, Absorbent dressing pad, Superabsorber, Gel, Other material, Foam, Fixation, Hydrocolloid, Film)
 - If other, specify
 - Was the compression applied? (Yes/No)
 - If yes, specify the tradename

6.4.2.5. Overall assessment of efficacy of study dressing

The following characteristics will be used as recorded in the CRF.

- Efficacy (Very good/ Good/ Moderate/ Poor/ Very poor)
- Tolerance with regard to perilesional skin (Very good/ Good/ Moderate/ Poor/ Very poor)
- Stagnating wound showed healing tendency (Very good/ Good/ Moderate/ Poor/ Very poor)
- Conformability of dressing to the wound (Very good/ Good/ Moderate/ Poor/ Very poor)
- Patient comfort (Very good/ Good/ Moderate/ Poor/ Very poor)
- Acceptability by patient (Very good/ Good/ Moderate/ Poor/ Very poor)

In addition, the following variables will be computed:

• Changes from D28 to D56 (stagnation/deterioration/improvement) – derived variables

6.4.2.6.Quality of life

- Pain Score (1 to 10) + numerical *derived variable*
- Mobility (1 to 10) + numerical derived variable
- Social life (1 to 10) + numerical derived variable
- Psychic aspect (1 to 10) + numerical derived variable

For each of the previous score, change from baseline at day 28 and day 56 will be computed as follows (QOL day 28 – QOL baseline, QOL day 56 – QOL baseline).

6.4.2.7.Overall quality of life

- How is your quality of life (1 to 10) categorical and numerical variables
- How satisfied are you with your overall quality of life (1 to 10) categorical and numerical variables

Change from baseline at day 28 and day 56 will be computed as follows (OQOL day 28 – OQOL baseline, OQOL day 56 – OQOL baseline).

